2. RESEARCH PLAN

Purpose of Study:
To compare scar infiltration with 0.5-1% Lidocaine at a dose of 3 mg/kg (max dose 300 mg) or scar deactivation with acupuncture surface release technique to determine which is more effective in reducing pain in adult patients with chronic, post-surgical pain related to the site of incision after low transverse Cesarean section compared to standard of care physical therapy with the McKenzie Method.
Hypotheses, Research Questions, or Objectives:

 • Objective 1: Compare whether a scar infiltration protocol with Lidocaine is more effective than scar deactivation with acupuncture surface release technique at improving pain in adults with chronic, post-surgical pain related to low transverse Cesarean section incision. • Null Hypothesis 1: 0.5-1% Lidocaine at a dose of 3 mg/kg (max dose 300 mg) does not reduce pain outcomes acutely and over time. • Null Hypothesis 2: Scar deactivation with acupuncture surface release technique does not reduce pain outcomes acutely and over time. • Alternative Hypothesis 1: 0.5-1% Lidocaine at a dose of 3 mg/kg (max dose 300 mg) reduces pain outcomes acutely and over time. • Alternative Hypothesis 2: Scar deactivation with acupuncture surface release technique reduces pain outcomes acutely and over time.
Significance:
According to CDC 2015 data, 32% of all births are delivered via Cesarean section ¹ . In patients who undergo Cesarean section, studies estimate 7-18% will experience chronic post-operative pain at the site of their incisional scar ² . These statistics indicate that up to 1 in 6 out of every pregnancy is at risk of developing postoperative pain with an increased risk with each subsequent Cesarean section, and a significant portion of these members will seek care in the primary care clinic.
Military Relevance:

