In 2016, the Department of Defense employed 1,288,596 active duty service members, of which 15.9% were women ³ . This age range is consistent with peak childbearing age, which extrapolates to a large portion of the female active duty force with the potential to have children during their military careers. Determining whether Scar infiltration or scar deactivation is more effective treatments for the reduction of chronic, post-surgical low transverse Cesarean section pain in military beneficiaries would result in less: lost duty days, profiles, and physical fitness testing exemptions in our active duty population, as well as an improved quality of life for all DoD beneficiaries. Scar infiltration is a technique using high dose and high volume lidocaine to infiltrate the scar. Scar infiltration uses 40cc to 60cc of 0.5% to 1% lidocaine, which is injected throughout the scar with a goal of 3-4mg/kg per injection. Typically a series of 4 to 5 injections. Scar deactivation is a technique when acupuncture needles are inserted into the skin surrounding the scar and are left in place for approximately 20 minutes and then removed. This can be repeated multiple times.

Background and Review of Literature:

Existing Knowledge: The etiology of chronic, post-surgical abdominal wall and/or pelvic pain after Cesarean section has multiple hypotheses. These possible sources include development of intra-peritoneal adhesions restricting fascial planes, anterior cutaneous nerve entrapment, and disruption of the autonomic nervous system within the intracellular fluid matrix known as an “interference field”^{2,4,5,6,7}. While there is not a clearly established and widely accepted pathophysiological cause to this post-operative pain, studies have estimated that between 7-33% of patients experience chronic peri-incisional pain after Cesarean section with Pfannenstiel incision – a type of abdominal surgical incision that allows access to the abdomen and the most common method for performing Cesarean sections today – defined as pain persisting beyond the period of expected healing, approximately 3 months^{2,7}.

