6. DATA ANALYSIS

Data Analysis:

Outcome Measures:

The primary outcome measures are the Patient and Observer Scar Assessment Scale (POSAS), and the Defense and Veterans Pain Rating Scale (DVPRS).

The Patient and Observer Scar Assessment Scale consists of the total score of two numeric scales measured by the patient and a qualified observer. Each scale assesses the scar by six characteristics on 10-point scales with a 1 corresponding to normal skin and a 10 representing the worst imaginable condition for that characteristic. The Total Score of both scales is calculated by summing scores of the six items resulting in a range of 6 to 60. The POSAS is treated as an interval variable; therefore, parametric methods will be used for this outcome¹⁷.

The DVPRS consists of an 11-point numerical rating scale with 0 indicating no pain and 10 indicating severe pain. It has been confirmed for reliability and validity in measuring both acute and chronic pain, and is currently the standard for pain measurement throughout DoD and VHA health systems. The DVPRS has demonstrated linear scale qualities allowing parametric methods to be used.^{18, 19}.

Outcome Measures:

Primary outcome: Pain reduction and reduction of DVPRS score. The goal for pain reductions will be 50% as a primary outcome.

Secondary outcomes: Reduction of POSAS score, improvement in related and unrelated symptoms as identified by above mentioned questionnaire, and willingness to undergo further treatment.

Sample Size Estimation/Power Analysis:

The study is organized as a mixed effects, randomized complete block design with repeated measures. Subject is a random effect as subjects will have been randomly subjected to C-section from the population of patients obtaining similar care at these Air Force medical treatment facilities, randomly enrolled from this population of patients, and randomly assigned to 3 treatment groups at the time of study enrollment. Fixed effects are treatment group and time of repeated measure as these effects cannot be generalized to other treatments and times.

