A priori power was assessed using G*Power Version 3.1.9.2.²⁰ Mean (SD) Total POSAS scores for non-hypertrophic scars resulting from vertical incisions have been found to be 21.1 (8.3) and 21.4 (7.4).^{21,22,23} Power for the Total POSAS score was assessed to detect a 1 SD difference. Mean (SD) DVPRS pain intensity for a broad sample consisting of inpatients and outpatients suffering from acute and chronic pain has been found to be 4.4 (2.4), and will serve as the effect size for this outcome.

A priori power analysis for a rANOVA for the POSAS indicates 24 subjects will have a power of 0.966 to detect the minimal clinically important difference at alpha = 0.05. A priori power analysis for a rANOVA for the DVPRS indicates 33 subjects will have a power of 0.962 to detect the minimal clinically important difference at alpha = 0.05. Post hoc tests within smaller subgroups may be required, such as differences due to time within a treatment group. Therefore, to achieve a power for post hoc tests of 0.95 at alpha = 0.05, a sample size of 45 subjects will be required.

Statistical Analysis:

Sample and treatment group means and standard deviations will be calculated for normally distributed interval variables and medians and interquartile ranges (IQR) for non-normally distributed interval variables. Frequency distributions will be produced for nominal and ordinal variables.

The statistical hypotheses of null effects for POSAS and DVPRS outcome measures will be tested by a mixed effects repeated measures analysis of covariance (rANCOVA). In the event the rANCOVA null hypothesis is rejected, contrasts will be used to investigate effects and differences within time intervals.

In the event multiple comparison tests are used to investigate effects, the Holm method will be used to correct the significance level of α to $p = .05$.²⁴

[name], Senior Research Biostatistician Subject Matter Expert for Clinical Research Management under contracts OMNI 0004 3-82 and OMNI 0005 3-126, is the statistical consultant supporting this study. Statistical analysis will be performed with R Version 3.5.1.²⁵

Number of Subjects:

	# Planned to Enroll	# Enrolled	# Planned to Complete Study	TOTAL
Number of Subjects at Scott AFB	30	N/A	24	
Number of Subjects at Nellis AFB	30	N/A	24	60

**If one site recruits more than the other, then they will be able to continue recruitment until the accrual ceiling has been reached.*

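### Null Hypotheses 1 and 2 name no comparator although Objective 1 is lidocaine versus acupuncture; the 0.95 behind 45 subjects ignores the planned Holm correction, and no pairwise between-arm power is stated.

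*Combined protocol and SAP*

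**What the plan says.** Section 2 (Research Plan) gives Objective 1 as: "Compare whether a scar infiltration protocol with Lidocaine is more effective than scar deactivation with acupuncture surface release technique at improving pain". The Military Relevance text repeats the question: "Determining whether Scar infiltration or scar deactivation is more effective treatments for the reduction of chronic, post-surgical low transverse Cesarean section pain". The Purpose statement adds a third arm as reference: "compared to standard of care physical therapy with the McKenzie Method".

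The hypotheses under that objective are of a different kind. Null Hypothesis 1 is that "0.5-1% Lidocaine at a dose of 3 mg/kg (max dose 300 mg) does not reduce pain outcomes acutely and over time". Null Hypothesis 2 is that "Scar deactivation with acupuncture surface release technique does not reduce pain outcomes acutely and over time". Neither names another arm, and the two alternatives mirror them.

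In section 6 (Data Analysis), the power text says "Fixed effects are treatment group and time of repeated measure". The Statistical Analysis text then plans a mixed-effects repeated measures ANCOVA, followed by contrasts if its null hypothesis is rejected, with Holm correction for multiple comparisons. It does not say which effect (group, time or group by time) must be rejected, which covariate is used, or which contrast answers Objective 1.

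The power text reports omnibus power for 24 subjects (POSAS, 0.966) and 33 subjects (DVPRS, 0.962). It then raises the number for post hoc tests, "such as differences due to time within a treatment group", and concludes that "to achieve a power for post hoc tests of 0.95 at alpha = 0.05, a sample size of 45 subjects will be required". The enrolment table plans 60 enrolled and 24 completers at each of two sites, so 48 completers.

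**The concern.** The objective is a comparison between arms, while the hypotheses can be read as before-after statements within an arm. Pain can fall in every arm through natural course or regression to the mean. A trial that tested the nulls as worded could then report that a treatment reduces pain and still have no evidence on its own objective. Because no contrast is tied to Objective 1, the deciding one could also be picked from three arms and five visits after the data are seen.

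The sample-size rationale does not close the gap. Its only example of a post hoc test is a time difference inside one arm, its alpha is 0.05 without adjustment although Holm is planned, and it reports no power for lidocaine versus acupuncture or for either against physical therapy.

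**Working it through.** **Inputs from the plan:** three arms; 45 subjects, power 0.95, alpha 0.05; a 1 SD difference (stated for POSAS); DVPRS SD 2.4; Holm correction; 48 completers (24 + 24).

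**Assumptions, not in the plan:** 1:1:1 allocation (15 per arm for 45, 16 for 48); two-sided tests; correlation r between visits of 0.3, 0.5 or 0.7. Triplets below follow that order. Power is from the noncentral t distribution unless noted.

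**1. Can the 0.95 be reproduced?** Two different tests give it.
- Paired test within one arm, n = 15, change of 1 SD of the differences: noncentrality = 1 × √15 = 3.873, 14 df, power 0.949.
- Three-arm between-factor omnibus test, five measurements, r = 0.5, one arm 1 SD from the other two: f = √2/3 = 0.471; λ = 45 × 0.2222 × 5 / (1 + 4 × 0.5) = 16.67; 2 and 42 df; power 0.951.

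The plan does not say which test, if either, was used.

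**2. What does Holm do to a power of 0.95?** Take any one-df test with exactly 0.95 at 0.05 and lower its alpha to the first Holm step.

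| Error df | Noncentrality for 0.95 | At 0.05/2 | At 0.05/3 |
|---|---|---|---|
| 14 (one arm) | 3.883 | 0.900 | 0.860 |
| 168 (3 × 14 × 4, pooled) | 3.626 | 0.913 | 0.885 |

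**3. What can reject the nulls as worded when the arms do not differ?** Let every arm fall by 0.5 SD (0.5 × 2.4 = 1.2 DVPRS points). The SD of change is √(2(1 − r)) = 1.183 / 1.000 / 0.775, so the standardised change is 0.423 / 0.500 / 0.645. Two paired tests with Holm, n = 15, simulated in 20,000 trials:
- No gate: at least one null rejected with probability 0.41 / 0.53 / 0.77.
- Gate on group by time (ANOVA of change across the three arms): about 0.04 at each correlation.
- A gate on time would protect little: with 45 subjects and five measures the time effect is itself rejected with probability 0.82 / 0.94 / 1.00.
- A baseline-adjusted lidocaine-versus-acupuncture contrast at alpha 0.05 rejects with probability about 0.05.

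**4. What power does the Objective 1 contrast have?** For one visit with a baseline covariate and a 1 SD difference, noncentrality = √(n/2) / √(1 − r²), with 2n − 3 df. For n = 15 this is 2.739 / √(1 − r²) = 2.871 / 3.162 / 3.835.

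| n per arm | Alpha 0.05 | Alpha 0.05/3 |
|---|---|---|
| 15 | 0.790 / 0.862 / 0.959 | 0.627 / 0.725 / 0.891 |
| 16 | 0.817 / 0.884 / 0.969 | 0.664 / 0.761 / 0.914 |

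Without the covariate, n = 15 gives 0.753 and 0.581.

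For the mean of four follow-ups with a baseline covariate, the residual variance is (1 + 3r)/4 − r² = 0.385 / 0.375 / 0.285. At 0.05/3 and n = 15:
- Constant 1 SD difference at all four visits: 0.962 / 0.967 / 0.993.
- Difference building 0.25, 0.5, 0.75, 1 SD (mean 0.625): 0.586 / 0.600 / 0.739.

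**The case against.** The planned analysis is not a pair of free-standing before-after tests. It is a model with treatment group as a fixed effect, and contrasts follow only a rejected model null. If the gate is group by time, the risk in step 3 is about 0.04. A reader might infer a false-claim risk of 0.41-0.77 from the wording of the nulls; that is the ungated case, and the plan does not commit to it. It does not exclude it either, since the gating effect is not named.

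A reader might also infer that 45 was sized for within-arm tests only. The sole example points that way, but it is introduced as an example, and a between-arm omnibus test reproduces the figure as well. Nor is there an arithmetic error: 0.95 is attainable on plausible inputs.

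The strongest inference would be that the trial is underpowered for Objective 1. The documents do not support that. An adjusted mean over four visits reaches 0.96 or more even at 0.05/3 if the difference is a constant 1 SD. Also, 0.05/3 is the strictest step: power under the full Holm procedure is at least that, and no split is needed if the Objective 1 contrast is the single primary test. Finally, the plan attaches 0.95 to post hoc tests in subgroups, so nobody is told that it is the power for Objective 1.

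All of this limits the size of the problem. None of it supplies the comparator, the contrast, the gate or the power.

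**Conclusion.** The point stands as a gap in the specification of hypotheses and contrasts, together with a stated power that does not match the planned multiplicity control. It should be fixed; it is not a reason to change enrolment.

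- The nulls do not express Objective 1. With equal arms, the chance of rejecting at least one runs from about 0.04 to 0.77, depending on a gating choice that the plan leaves open. This rests on an assumed common fall of 0.5 SD and correlations of 0.3-0.7.
- The 0.95 does not hold at the first Holm step. It becomes 0.90-0.91 for two comparisons and 0.86-0.89 for three, for any one-df test with 14 to 168 error df.
- No power is stated for any pairwise between-arm contrast. What the trial has depends on the contrast and the alpha, neither of which is named.

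**What to change.** Keep the enrolment and change the wording.

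1. Restate Null Hypotheses 1 and 2 as between-arm statements on DVPRS: lidocaine versus acupuncture, and each versus physical therapy. Label within-arm before-after tests descriptive. Only the two needle arms have pre- and post-treatment values at the same visit, so make any acute contrast a separate lidocaine-versus-acupuncture one.
2. Name one baseline-adjusted lidocaine-versus-acupuncture DVPRS contrast from the rANCOVA as the test of Objective 1. It can be Visit 5, or the mean of Visits 2-5 using the pre-treatment value at Visits 2-4 in the needle arms; the choice is the sponsor's. State whether it is tested alone at 0.05 or inside the Holm family.
3. Replace the 0.95 sentence with the power of that contrast for 45-48 completers, giving the difference, correlation, covariate and alpha. For 1 SD at Visit 5 it is 0.79-0.97 alone at 0.05, or 0.63-0.91 at 0.05/3. If the mean is chosen and tested at 0.05/3 with 15 per arm, say that 0.96-0.99 needs a constant 1 SD difference and that a building effect gives 0.59-0.74.

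The cost is text only, with no extra patients or visits. The stated power may look less favourable, and an average answers the question over follow-up rather than at week 20.

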3. RESEARCH DESIGN AND METHODS

Research Design and Methods:

Active duty members and DoD beneficiaries, age 18 years of age or older, meeting the inclusion/exclusion criteria will be offered an opportunity to participate. They will be recruited from the clinics located at Nellis AFB and Scott AFB. All of the below items are research-related unless marked as 'standard of care':

Pre-Eligibility review: Subjects who responded to advertisements or recruitment letters or have given their permission to be contacted will be approached by a study staff member to discuss the subject's interest in the research study and to receive a pre-eligibility screening for study participation. The attached "Pre-Eligibility Review Script" will be used and response will be recorded. If the subject is interested in participating in the study, the study staff member will schedule a screening visit while the subject waits on the phone or in-person, in order to confirm the schedule appointment with the subject. Following the pre-screening procedure, the script will be shredded.

Screening Visit:

- Obtain and document signed Informed Consent document and HIPAA Authorization.
- Review past medical history to verify the inclusion/exclusion criteria including previous encounter, medication list (including analgesic medication currently taking), co-morbidities, demographics, and problems list.

- Record date of birth, age, gender, race, ethnicity, DoD ID, current email address, height (inches), weight (in pounds-not stated weight), obstetrical history, history of relevant pain and interventions.
- Instruct subjects to discontinue any current acupuncture treatment at the onset of entering the study. It is theorized that any acupuncture treatment can have a positive or a negative effect on treatment response regardless of the technique or treatment indication.
- If the subject is an active duty member, we will ask:
 - Have you or are you currently on a fitness restriction for this condition.
 - If so, what are/were the dates of the restriction?

Randomization:

- Subjects will be randomized into one of three research-related treatment groups using block randomization with repeated measures:
 - **Group 1: Scar Deactivation Surface Release Technique protocol:**

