- Subjects will be weighed (in pounds-not stated weight).
- We will ask what the subjects' expectations are regarding lidocaine's effectiveness for chronic, post-surgical pain related to low transverse Cesarean Section.
- The Research Coordinator will document the total volume of 0.5-1% Lidocaine injection.
- **Pre-Treatment:**
 - DVPRS

- Instruct patients to mark general area of scar on pictures provided on the POSAS Patient Scale.
- Instruct the PI or AI to complete the POSAS Observer Scale.
- Post-Treatment:
 - DVPRS
 - Instruct patients to mark general area of scar on pictures provided the POSAS Patient Scale.
 - Instruct the PI or AI to complete the POSAS Observer Scale.

Group 3: Physical Therapy:

- Study staff will reconcile medication list (including analgesic medication currently taking).
- Subjects will be weighed (in pounds-not stated weight).
- We will ask what the subjects' expectations are regarding physical therapy's effectiveness for chronic, post-surgical pain related to low transverse Cesarean Section.
- Subjects will be given a study diary and asked to track the dates and duration of their physical therapy treatments.
- DVPRS
- Instruct patients to mark general area of scar on pictures provided on the POSAS Patient Scale.
- Instruct the PI or AI to complete the POSAS Observer Scale.

Visit 2 (4 weeks after visit 1 (visit window plus or minus 1 week)):

Group 1: Scar Deactivation Surface Release Technique protocol (acupuncture):

- Study staff will reconcile medication list (including analgesic medication currently taking).
- Subjects will be weighed (in pounds-not stated weight).
- The Research Coordinator will record the number of needles placed and the name of the provider performing the acupuncture.
- Pre-Treatment:
 - DVPRS
 - Instruct patients to mark general area of scar on pictures provided on the POSAS Patient Scale.
 - Instruct the PI or AI to complete the POSAS Observer Scale.
- Post-Treatment:
 - DVPRS
 - Instruct patients to mark general area of scar on pictures provided the POSAS Patient Scale.
 - Instruct the PI or AI to complete the POSAS Observer Scale.

Group 2: Scar Infiltration with 0.25-1% Lidocaine:

- Study staff will reconcile medication list (including analgesic medication currently taking).
- Subjects will be weighed (in pounds-not stated weight).
- The Research Coordinator will document the total volume of 0.5-1% Lidocaine injection.
- Pre-Treatment:
 - DVPRS

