 - Instruct patients to mark general area of scar on pictures provided on the POSAS Patient Scale.
 - Instruct the PI or AI to complete the POSAS Observer Scale.
- Post-Treatment:
 - DVPRS
 - Instruct patients to mark general area of scar on pictures provided the POSAS Patient Scale.
 - Instruct the PI or AI to complete the POSAS Observer Scale.

Group 3: Physical Therapy:

- Study staff will reconcile medication list (including analgesic medication currently taking).
- Subjects will be weighed (in pounds-not stated weight).
- We will record the information from the study diary and remind them to track the dates and duration of their physical therapy treatments.
- DVPRS
- Instruct patients to mark general area of scar on pictures provided on the POSAS Patient Scale.

- Instruct the PI or AI to complete the POSAS Observer Scale.

Visit 3 (8 weeks after visit 1) (visit window plus or minus 1 week):

Group 1: Scar Deactivation Surface Release Technique protocol (acupuncture):

- Study staff will reconcile medication list (including analgesic medication currently taking).
- Subjects will be weighed (in pounds-not stated weight).
- The Research Coordinator will record the number of needles placed and the name of the provider performing the acupuncture.
- ***Pre-Treatment:***
 - DVPRS
 - Instruct patients to mark general area of scar on pictures provided on the POSAS Patient Scale.
 - Instruct the PI or AI to complete the POSAS Observer Scale.
- ***Post-Treatment:***
 - DVPRS
 - Instruct patients to mark general area of scar on pictures provided the POSAS Patient Scale.
 - Instruct the PI or AI to complete the POSAS Observer Scale.

Group 2: Scar Infiltration with 0.25-1% Lidocaine:

- Study staff will reconcile medication list (including analgesic medication currently taking).
- Subjects will be weighed (in pounds-not stated weight).
- The Research Coordinator will document the total volume of 0.5-1% Lidocaine injection.
- ***Pre-Treatment:***
 - DVPRS
 - Instruct patients to mark general area of scar on pictures provided on the POSAS Patient Scale.
 - Instruct the PI or AI to complete the POSAS Observer Scale.
- ***Post-Treatment:***
 - DVPRS
 - Instruct patients to mark general area of scar on pictures provided the POSAS Patient Scale.
 - Instruct the PI or AI to complete the POSAS Observer Scale.

Group 3: Physical Therapy:

- Study staff will reconcile medication list (including analgesic medication currently taking).

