- Subjects will be weighed (in pounds-not stated weight).
- We will record the information from the study diary and remind them to track the dates and duration of their physical therapy treatments.
- DVPRS
- Instruct patients to mark general area of scar on pictures provided on the POSAS Patient Scale.
- Instruct the PI or AI to complete the POSAS Observer Scale.

Visit 4 (16 weeks after visit 1) (visit window plus or minus 1 week):

Group 1: Scar Deactivation Surface Release Technique protocol (acupuncture):

- Study staff will reconcile medication list (including analgesic medication currently taking).
- Subjects will be weighed (in pounds-not stated weight).
- The Research Coordinator will record the number of needles placed and the name of the provider performing the acupuncture.
- ***Pre-Treatment:***
 - DVPRS
 - Instruct patients to mark general area of scar on pictures provided on the POSAS Patient Scale.
 - Instruct the PI or AI to complete the POSAS Observer Scale.
- ***Post-Treatment:***
 - DVPRS
 - Instruct patients to mark general area of scar on pictures provided the POSAS Patient Scale.

- Instruct the PI or AI to complete the POSAS Observer Scale.

Group 2: Scar Infiltration with 0.25-1% Lidocaine:

- Study staff will reconcile medication list (including analgesic medication currently taking).
- Subjects will be weighed (in pounds-not stated weight).
- The Research Coordinator will document the total volume of 0.5-1% Lidocaine injection.
- Pre-Treatment:
 - DVPRS
 - Instruct patients to mark general area of scar on pictures provided on the POSAS Patient Scale.
 - Instruct the PI or AI to complete the POSAS Observer Scale.
- Post-Treatment:
 - DVPRS
 - Instruct patients to mark general area of scar on pictures provided the POSAS Patient Scale.
 - Instruct the PI or AI to complete the POSAS Observer Scale.

Group 3: Physical Therapy:

- Study staff will reconcile medication list (including analgesic medication currently taking).
- Subjects will be weighed (in pounds-not stated weight).
- We will record the information from the study diary and remind them to track the dates and duration of their physical therapy treatments.
- DVPRS
- Instruct patients to mark general area of scar on pictures provided on the POSAS Patient Scale.
- Instruct the PI or AI to complete the POSAS Observer Scale.

Visit 5 (20 weeks after visit 1) (visit window plus or minus 1 week):

Group 1: Scar Deactivation Surface Release Technique protocol (acupuncture):

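### The 0.95 post hoc power that justifies 45 subjects is stated at alpha = 0.05 with no correction named, although post hoc comparisons will be Holm-corrected over a family of unstated size

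*Combined protocol and SAP*

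**What the plan says.** Section 6, Sample Size Estimation/Power Analysis, first gives power for the overall repeated-measures tests: 0.966 with 24 subjects for POSAS and 0.962 with 33 for DVPRS, both at alpha 0.05. It then anticipates follow-up tests: "Post hoc tests within smaller subgroups may be required, such as differences due to time within a treatment group". From this it concludes that "to achieve a power for post hoc tests of 0.95 at alpha = 0.05, a sample size of 45 subjects will be required". So the rise from 33 to 45 rests on the post hoc tests alone.

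Under Statistical Analysis in the same section, if the rANCOVA null hypothesis is rejected, "contrasts will be used to investigate effects and differences within time intervals". If that leads to multiple comparison tests, "the Holm method will be used to correct the significance level".

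The contrasts are not listed or counted. Nor does the plan say whether the Holm family runs across arms, across visits, or across POSAS and DVPRS together.

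Section 3 shows how many tests could arise. "Subjects will be randomized into one of three research-related treatment groups", and follow-up is at "Visit 2 (4 weeks after visit 1"), "Visit 3 (8 weeks after visit 1"), "Visit 4 (16 weeks after visit 1") and Visit 5 at week 20. The number-of-subjects table plans 60 enrolled and 24 + 24 = 48 completing.

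**The concern.** A power figure describes a test at a given significance level. The post hoc sentence uses the same alpha of 0.05 as the two single overall tests and mentions no adjustment. Holm is stricter: with m tests, the smallest p-value is compared with 0.05/m, the next with 0.05/(m − 1), and so on. Once two or more post hoc tests are run, each has less power than the same test at 0.05.

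Because 45 is derived from this figure, a reader will take 0.95 as the power of the tests that will be carried out. Without the family size, the reader cannot tell whether the corrected power is close to 0.95 or well below it. Leaving the family open also means that it could be settled after the data are seen.

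**Working it through.** **Inputs from the documents:** 45 subjects, three arms, alpha 0.05, four visits after Visit 1, and 48 planned completers. The 1 SD difference is stated for POSAS; carrying it over to the post hoc test is an assumption.

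**Further assumptions (the documents give none of these):** equal allocation (45/3 = 15 per arm; 48/3 = 16), two-sided tests, and correlation ρ = 0.5 between visits.

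**Formula.** The SD of a within-subject change is SD × √(2(1 − ρ)), which equals the score SD at ρ = 0.5. For a 1 SD change the t statistic has noncentrality √n, so √15 = 3.873 at 15 per arm. Power is the noncentral-t probability beyond the two-sided critical value.

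**The plan's own figure.** A paired test with n = 15, df 14 and alpha 0.05 gives 0.949, in line with 0.95 and with no correction applied. The match is not unique: a between-group repeated-measures ANOVA with N = 45, f = 0.471, five measurements and ρ = 0.5 gives 0.950.

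**Possible family sizes.** Three tests: one change from Visit 1 in each arm. Twelve tests: 3 arms × 4 follow-up visits. Twelve is not the maximum. Groups 1 and 2 are measured before and after treatment at Visits 1 to 4 and once at Visit 5 (4 × 2 + 1 = 9), and Group 3 is measured five times. That allows 8 + 8 + 4 = 20 changes from the first measurement for each outcome.

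**Two ends of the range.** The first Holm step uses 0.05/m (0.0167 for three tests, 0.00417 for twelve). It is a lower bound, because any p-value below it is always rejected. The favourable end is the full Holm procedure with every change truly 1 SD. It was simulated with 20,000 runs under compound symmetry for 15 per arm, and for twelve tests with 16 per arm.

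| Per arm | Error term | Uncorrected | 3 tests: first step | 3 tests: all real | 12 tests: first step | 12 tests: all real |
|---|---|---|---|---|---|---|
| 15 | paired, df 14 | 0.949 | 0.858 | 0.939 | 0.670 | 0.858 |
| 15 | pooled over arms, df 42 | 0.966 | 0.911 | 0.960 | 0.793 | 0.926 |
| 16 | paired, df 15 | 0.962 | 0.887 | 0.956 | 0.720 | 0.895 |
| 16 | pooled over arms, df 45 | 0.975 | 0.930 | about 0.97 | 0.829 | 0.945 |

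**Sensitivity to correlation.** With 15 per arm and pooled error (df 42), ρ from 0.3 to 0.7 gives 0.89 to 0.998 uncorrected. At the first Holm step it gives 0.78 to 0.99 for three tests and 0.60 to 0.97 for twelve. The assumed correlation therefore matters as much as the family size.

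**The case against.** The power sentence is silent on correction; it does not say that there was none. The alpha of 0.05 could be meant as the familywise level that Holm protects, and the plan does not name the test behind 0.95. Some corrected values do reach about 0.95 at 45 subjects, such as 0.960 for three tests with pooled error and all effects real. This stands in part: uncorrected is the natural reading, since the same wording is used for the single overall tests, but it is not the only one. Even on the other reading, the number of tests behind the figure is missing.

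The loss may also be small. The favourable three-test case falls only from 0.949 to 0.939 with a paired test, and the 48 planned completers recover more than that. This stands, and it is why no single corrected figure can be given.

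Finally, the post hoc tests are conditional on a rejected overall test, and Holm is specified in advance. Error control within a family is therefore provided for once the family is fixed. That limits the point to the power statement. It does not remove it, because the plan chose to set its sample size on these tests.

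A reader might go further and infer that 45 is too few, that the sponsor miscalculated, or that 0.95 cannot hold for the lidocaine-versus-acupuncture comparison in Objective 1. The documents support none of these. Adequacy depends on unstated inputs, more than one set of inputs reproduces 0.95, and the plan does not say which contrast the figure refers to.

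**Conclusion.** The point holds as a defect in the power statement. On its natural reading, 0.95 is an uncorrected figure and overstates the power of the Holm-corrected post hoc tests whenever more than one is run.

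Under the paired-test assumptions with 15 per arm, 0.949 becomes 0.86 to 0.94 for three tests and 0.67 to 0.86 for twelve. With error pooled over arms, 0.966 becomes 0.91 to 0.96 and 0.79 to 0.93. With 16 per arm the shortfall is smaller, and for a small family it may be negligible.

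These ranges rest on equal allocation, two-sided testing, a 1 SD change and ρ = 0.5. Twelve is one possible family, neither the plan's choice nor the schedule's maximum. The ranges show that the stated figure cannot be interpreted without a family size; they do not show that the trial is underpowered. It should be fixed, as a matter of wording.

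**What to change.** Revise the power text in section 6:

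- Name and count the post hoc contrasts that form the Holm family for each outcome, before any data are analysed.
- Replace 0.95, or label it as uncorrected. If a correction was already built in, say so and give the number of tests.
- Give the Holm-corrected power for that family at 45 subjects and at the 48 planned completers, as a range from the first Holm step to all effects real. State the error term and correlation assumed.

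This changes wording only: enrolment, visits and the analysis model stay as they are. The cost is that the sponsor must commit to a list of contrasts and a correlation, and that the stated post hoc power may become less favourable.
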